8. RESEARCH QUESTION AND OBJECTIVES

The research questions that could be addressed by this study are:

What proportions of SARS-CoV-2 diagnosed patients have a diagnosis of RA, PsA, or UC (ie, indicated subcohorts) or not (ie, non-indicated subcohort) and what is risk of serious clinical manifestations and outcomes of interest in these subcohorts?

Within the indicated subcohorts of SARS-CoV-2 diagnosed patients, what is the proportion treated at baseline with the following systemic therapies: tofacitinib, JAK inhibitors, TNFi, non-TNFi, and csDMARD and what is risk of serious clinical manifestations and outcomes of interest within strata?

Primary objectives:

- Within subcohorts of SARS-CoV-2 diagnosed patients, determine the proportions of patients with a diagnosis of RA, PsA, and UC (indicated subcohorts) and patients without any of these conditions (non-indicated subcohort).
- For each indicated subcohort and non-indicated subcohort, describe baseline demographic characteristics, treatment history and comorbidities.
- Within each indicated subcohort and non-indicated subcohort, estimate proportion experiencing serious clinical manifestations and outcomes of interest (Section 9.3).
- Within each indicated subcohort of SARS-CoV-2 diagnosed patients, determine the proportions of patients treated with the following systemic therapies (class) at baseline: tofacitinib, JAK inhibitors, TNFi, non-TNFi and csDMARD (as monotherapy and combination therapy, as applicable).

- Describe patient characteristics, treatment history and comorbidities within baseline treatment strata.
- Estimate risk of serious clinical manifestations and outcomes of interest within baseline treatment strata (Section 9.3).
- Determine the proportions of patients that continue baseline treatment after SARS-CoV-2 diagnosis within indicated subcohorts.

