9.3. Variables

Variable	Role	Operational definition ^a
SARS-CoV-2 Diagnosis	Inclusion criteria	SARS-CoV-2 diagnosis.
Rheumatoid Arthritis	Subcohort identification	RA diagnosis in baseline period.
Psoriatic Arthritis	Subcohort identification	PsA diagnosis in baseline period.
Ulcerative Colitis	Subcohort identification	UC diagnosis in baseline period.
Non-indicated subcohort	Inclusion criteria/Subcohort identification	Absence of RA, PsA, and UC codes within baseline period.
SARS-CoV-2 Diagnosis Date	Exposure/Index date	Date associated with SARS-CoV-2 diagnosis.
Baseline systemic therapy	Baseline Characteristic/Exposure	Evidence of therapy prescribed 6 months prior to index date.
		Categorical: csDMARD, TNFi, non- TNFi, tofacitinib, JAK inhibitor (as monotherapy or combination therapy).
Baseline csDMARD	Baseline Characteristic/Exposure (Comedication)	Evidence of therapy prescribed within 6 months prior to index date.
Baseline TNFi	Baseline Characteristic/Exposure	Evidence of therapy prescribed within 6 months prior to index date.
Baseline Non-TNFi	Baseline Characteristic/Exposure	Evidence of therapy prescribed within 6 months prior to index date.
Baseline bDMARD	Baseline Characteristic/Exposure	TNFi or non-TNFi prescribed within 6 months prior to index date.
Baseline tofacitinib	Baseline characteristic/Exposure	Tofacitinib Evidence of therapy prescribed within 6 months prior to index date.
Baseline JAK inhibitor	Baseline Characteristic/Exposure	Evidence of therapy prescribed within 6 months prior to index date.
Baseline Monotherapy	Baseline characteristic/Exposure	No evidence of MTX or other csDMARD concomitant with baseline advanced systemic therapy (ie, TNFi, non-TNFi, tofacitinib, JAK inhibitor).
Baseline Combination therapy	Baseline characteristic/Exposure	Evidence of MTX or other csDMARD concomitant with baseline advanced systemic therapy (ie, tofacitinib, bDMARD, JAK inhibitor, csDMARD) and MTX or other csDMARD.

Variable	Role	Operational definition ^a
Post-SARS systemic therapy	Baseline Characteristic/Exposure	Evidence of therapy prescribed within 6 months after index date.
		Categorical: csDMARD, TNFi, non-TNFi, tofacitinib, JAK inhibitor (as monotherapy or combination therapy).
Post-SARS csDMARD	Baseline Characteristic/Exposure (Comedication)	Evidence of therapy prescribed within 6 months on or after index date.
Post-SARS TNFi	Baseline Characteristic/Exposure	Evidence of therapy prescribed within 6 months on or after index date.

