9.4. Data Sources

The structured data within Optum COVID testing database will be used to identify populations, exposures, confounders and endpoints of interest as described in Section 9.3.

As of 22 April 2020 the Optum COVID database currently includes 32,000 patients who have either been tested for COVID-19 or diagnosed with COVID-19 (regardless of positive/negative result). Refreshes of this data are delivered on a bi-weekly basis through September 2020 and on a monthly cadence from October 2020 – February 2021. This cohort includes details of a patient's office visit and/or hospital stay, including but not limited to: demographic, diagnosis, procedures performed, vital signs and other biometric measures, laboratory results, and prescriptions written and dispensed. All diagnosis data in this study will be obtained from structured data (via ICD-10-CM codes or ICD-9-CM codes where applicable). All drug treatment data will be pulled from prescription written, medication administration, and procedure tables when appropriate (via ICD-9-CM or ICD-10-CM, NDC, CPT, and HCPCS codes).

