- As part of a shared decision-making process between patients and rheumatology providers, select measures to reduce healthcare encounters and potential exposure to SARS-CoV-2 (beyond general preventive measures) may be reasonable, eg, reduced frequency of lab monitoring, optimal use of telehealth, increased dosing intervals between intravenous medications) (M/H).
- If indicated, glucocorticoids should be used at the lowest dose possible to control rheumatic disease, regardless of exposure or infection status (M/H).
- Glucocorticoids should not be abruptly stopped, regardless of exposure or infection status (H).
- If indicated, angiotensin converting enzyme (ACE) inhibitors or angiotensin receptor blockers (ARBs) should be continued in full doses or initiated (M/H).

ONGOING TREATMENT OF STABLE PATIENTS IN THE ABSENCE OF **INFECTION OR SARS-COV-2 EXPOSURE:**

- Hydroxychloroquine or chloroquine (HCQ/CQ), sulfasalazine (SSZ), methotrexate (MTX), leflunomide (LEF), immunosuppressants (eg, tacrolimus, cyclosporine, mycophenolate mofetil, azathioprine), biologics, Janus kinase (JAK) inhibitors and non-steroidal anti-inflammatory drugs (NSAIDs) may be continued (this includes patients with giant cell arteritis with an indication, in whom IL-6 inhibitors should be continued, if available) (M/H).
- Denosumab may still be given, extending dosing intervals to no longer than every 8 months, if necessary to minimize healthcare encounters (M).
- For patients with a history of vital organ-threatening rheumatic disease, immunosuppressants should not be dose-reduced (M).

IN PATIENTS WITH SLE:

• In newly diagnosed disease, HCQ/CQ should be started at full dose, when available (H).

- In pregnant women with SLE, HCQ/CQ should be continued at the same dose, when available (H).
- If indicated, belimumab may be initiated (M).

TREATMENT OF NEWLY DIAGNOSED OR ACTIVE RHEUMATIC DISEASES, IN THE ABSENCE OF INFECTION OR SARS-COV-2 EXPOSURE:

Active Inflammatory Arthritis:

- For patients well-controlled on HCQ/CQ, this disease-modifying anti-rheumatic drug (DMARD) should be continued, when available; when unable to access (including in patients with active or newly diagnosed disease), switching to a different conventional synthetic DMARD (either as monotherapy or as part of combination therapy) should be considered (M/H).

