- For patients well-controlled on an IL-6 inhibitor, this DMARD should be continued, when available; when unable to access the agent, switching to a different biologic should be considered (M). The panel noted uncertainty regarding the use of JAK inhibitors in this situation.
- For patients with moderate to high disease activity despite optimal conventional synthetic DMARDs, biologics may be started (H). The panel noted uncertainty regarding the use of JAK inhibitors in this situation.
- For active or newly diagnosed inflammatory arthritis, conventional synthetic DMARDs may be started or switched (M).
- If indicated, low-dose glucocorticoids (≤10 mg prednisone equivalent) or NSAIDs may be started (M/H).

Other Rheumatic Diseases:

- In patients with systemic inflammatory or vital organ-threatening disease (eg, lupus nephritis or vasculitis), high-dose glucocorticoids or immunosuppressants may be initiated (M).
- In patients with newly diagnosed Sjögren's, given the paucity of data proving efficacy, HCQ/CQ should not be started (M).

ONGOING TREATMENT OF STABLE PATIENTS FOLLOWING SARS-COV-2 EXPOSURE (WITHOUT SYMPTOMS RELATED TO COVID-19):

• HCQ, SSZ, and NSAIDs may be continued (M/H).

Redacted

- Immunosuppressants, non-IL-6 biologics, and JAK inhibitors should be stopped temporarily, pending a negative test result for COVID-19 or after 2 weeks of symptom-free observation (M). The panel noted uncertainty re: temporarily stopping MTX or LEF in this situation.
- In select circumstances, as part of a shared decision-making process, IL-6 inhibitors may be continued (M).

RHEUMATIC DISEASE TREATMENT IN THE CONTEXT OF DOCUMENTED OR PRESUMPTIVE COVID-19 INFECTION:

- Regardless of COVID-19 severity, anti-malarial therapies (HCQ/CQ) may be continued, but SSZ, MTX, LEF, immunosuppressants, non-IL-6 biologics, and JAK inhibitors should be stopped or held (M/H).
- For patients with severe respiratory symptoms, NSAIDS should be stopped (M). The panel demonstrated low consensus with regards to stopping NSAIDs in the absence of severe symptoms.
- In select circumstances, as part of a shared decision-making process, IL-6 inhibitors may be continued (M).

Updated April 14, 2020

Document Approval Record

Document Name:	A3921380_Protocol Amendment 2 28 August 2023	Version 3.0 (clean)_COVID PASS_
Document Title:	A3921380_Protocol Amendment 2 28 August 2023	Version 3.0 (clean)_COVID PASS_
Signed By:	Date(GMT)	Signing Capacity
Redacted

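### Any prescription in the 6 months before diagnosis counts as baseline treatment, so patients who had already stopped or switched enter the treatment strata and can appear to stop after COVID-19

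*Protocol*

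**What the plan says.** Protocol Section 9.3 defines baseline csDMARD, TNFi, non-TNFi, tofacitinib and JAK inhibitor use with the same phrase: "Evidence of therapy prescribed within 6 months prior to index date". The overall baseline therapy variable uses nearly the same words, "Evidence of therapy prescribed 6 months prior to index date". Neither sets a condition on recency, days' supply, dispensing or use on the index date.

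Section 9.4 names the exposure sources: "All drug treatment data will be pulled from prescription written, medication administration, and procedure tables when appropriate". The same section says that the data include "laboratory results, and prescriptions written and dispensed", but it names no dispensing table as a source of exposure.

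The post-index class variables mirror the baseline ones: "Evidence of therapy prescribed within 6 months on or after index date".

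Two of the primary objectives in Section 8 rest on these variables. One is the risk of serious outcomes within baseline treatment strata. The other is "Determine the proportions of patients that continue baseline treatment after SARS-CoV-2 diagnosis within indicated subcohorts".

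**The concern.** One prescription written about 170 days before diagnosis and never renewed counts the same as use on the day of diagnosis.

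The protocol itself makes stopping or switching an expected path. Section 7 describes tofacitinib as indicated after inadequate response or intolerance to methotrexate, other DMARDs or TNF blockers, depending on the disease. A recent switcher has 6-month evidence of both the old and the new drug, and Section 9.3 gives no rule for which one is current.

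Two results are at stake:

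- **Stratum risk.** It is read as the risk in patients on the drug, but it mixes current and former users.
- **Continuation.** A patient who stopped before diagnosis sits in the denominator and, with no later prescription, looks like someone who stopped because of COVID-19.

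Section 9.9 acknowledges misclassification of comorbidities and risk factors that fall outside the baseline period. It says nothing about drug exposure.

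**Working it through.** The protocol gives no discontinuation, continuation or stratum-risk figure, so there is nothing to reproduce. The steps below show how the rule behaves under stated assumptions.

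**Inputs from the protocol:** a 6-month look-back (taken as 183 days); one prescription is enough; post-index treatment requires a prescription on or after index.

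**Assumed inputs:** days' supply of 30 or 90; discontinuation of 2%, 5% or 10% per month; true continuation of 60% among current users; outcome risk of 20% on drug.

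**1. Longest time off drug while still counted as treated** = 183 − supply.
- 30 days' supply: 183 − 30 = 153 days, or 84% of the window.
- 90 days' supply: 183 − 90 = 93 days, or 51%.

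**2. Share m of a stratum off drug at index.** With a steady number of current users, q = monthly discontinuation × (183 − supply)/30.4 is the number of former users in the window per current user, and m = q/(1 + q).

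| Discontinuation per month | m, 30-day supply | m, 90-day supply |
|---|---|---|
| 2% | 9% | 6% |
| 5% | 20% | 13% |
| 10% | 34% | 23% |

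Example: 0.05 × 153/30.4 = 0.252, and 0.252/1.252 = 20%. A working range of 10% to 30% is therefore plausible under these inputs, but the protocol does not establish it.

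**3. Continuation.** Observed = (1 − m) × c + m × r, where c is true continuation among current users and r is the share of off-drug patients prescribed the drug again after index. With c = 60% and r = 0:
- m = 10%: 0.90 × 60% = 54%
- m = 20%: 0.80 × 60% = 48%
- m = 30%: 0.70 × 60% = 42%

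The result depends on r. At m = 20% and r = 30%, observed = 48% + 6% = 54%. At r = 60% there is no bias.

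**4. Stratum risk.** Observed = (1 − m) × risk on drug + m × risk off drug.
- Off-drug risk 10%: m = 10% gives 18% + 1% = 19%; m = 30% gives 14% + 3% = 17%.
- Off-drug risk 30%: m = 10% gives 18% + 3% = 21%; m = 30% gives 14% + 9% = 23%.

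The shift goes towards the off-drug risk, in a direction the protocol does not let us predict.

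**The case against.** **This is SAP territory.** The footnote to the Section 9.3 table leaves codes and other definitions to the SAP, and Section 9.7 lets the SAP modify the plan. The SAP may add a current-use rule or define continuation, which the protocol does not do. This stands in part. However, the protocol itself fixes both the window and the prescribing criterion. Section 9.2.3, by contrast, expressly leaves the baseline period for the RA, PsA or UC diagnosis to the SAP. Followed as written, the rule has the effect described.

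**The study is descriptive.** Section 9.9 rules out inference on treatment associations, and the 6-month window matches the enrolment criterion and the covariate window. That softens the consequence. A descriptive risk is still mislabelled if part of the stratum is not on the drug, and Section 7 states the broader aim of assessing whether tofacitinib modifies risk.

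**Stronger readings that the protocol does not support:**

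- A reader might infer that JAK inhibitor strata are diluted more than csDMARD strata, because Appendix 1 says "Immunosuppressants, non-IL-6 biologics, and JAK inhibitors should be stopped temporarily, pending a negative test result for COVID-19". The same sentence gives two weeks of symptom-free observation as the alternative end of the hold, so many of these patients are recent users. The appendix also notes uncertainty about holding methotrexate or leflunomide after exposure, lets all these classes continue in stable unexposed patients, and covers rheumatic disease but not UC. Unequal dilution is possible but not shown.
- A reader might count everyone who never filled a prescription as a later stopper. A never-filler who is prescribed the drug again after index would count as continuing. Recorded administrations were given, so non-filling applies only to written prescriptions.
- A reader might take the continuation error to run only downward. A patient who pauses at infection and restarts within 6 months counts as continuing.

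**Conclusion.** The concern holds in a limited form. The 6-month prescribing rule has no recency or coverage condition. It therefore places patients who stopped or switched before diagnosis in the treatment strata and in the natural denominator for continuation, where the post-SARS variables make those without a later prescription look like post-diagnosis stoppers. The limitations section does not disclose this.

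The size is unknown. The drop from 60% to between 54% and 42% rests on 10% to 30% of a stratum being off drug at index, on none of them being prescribed the drug again, and on continuation being read from the post-SARS variables. None of these figures comes from the protocol. Neither the direction of the effect on stratum risks nor a difference in dilution between classes can be established from the document.

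**What to change.** - **Section 9.3, baseline use.** Keep the 6-month definition and add a current-use definition beside it: the latest written, dispensed or administered record covers the index date by days' supply where recorded, and otherwise by a fixed class-specific interval, plus a stated grace period. The grace period must be long enough for the "increased dosing intervals between intravenous medications" that Appendix 1 allows, or infused patients on stretched schedules would be classed as off drug. Use the dispensing records mentioned in Section 9.4 where they exist.
- **Section 9.7.** Report stratum risks under both definitions.
- **Continuation.** Define it explicitly and use current users as the denominator.
- **Section 9.9.** Name misclassification of drug exposure as a limitation.

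A flag for supply ending shortly before index would not identify guidance-driven holds. A temporary hold leaves the recorded supply unchanged, so such a flag would pick up late refills and miss real holds.

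**Cost:** a definitional and programming change on existing data. The current-use strata will be smaller. The protocol does not list days' supply as a data element, so an assumed interval will be needed where it is missing.

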Post-SARS Non-TNFi	Baseline Characteristic/Exposure	Evidence of therapy prescribed within 6 months on or after index date.
Post-SARS bDMARD	Baseline Characteristic/Exposure	Evidence of TNFi or non-TNFi on or after index date.
Post-SARS tofacitinib	Baseline characteristic/Exposure	Evidence of therapy prescribed within 6 months on or after index date.
Post-SARS JAK inhibitor	Baseline Characteristic/Exposure	Evidence of therapy prescribed within 6 months on or after index date.
Post-SARS Monotherapy	Baseline characteristic/Exposure	No evidence of MTX or other csDMARD concomitant with post-index advanced systemic therapy (ie, TNFi, non-TNFi, tofacitinib, JAK inhibitor).
Post-SARS Combination therapy	Baseline characteristic/Exposure	Evidence of MTX or other csDMARD concomitant with post-index advanced systemic therapy (ie, bDMARD, tDMARD) and MTX or other csDMARD.
Region	Baseline/potential confounder	Distribution of geographic region at index date.
Insurance	Baseline/potential confounder	Insurance type at index date.
Age	Baseline/potential confounder/risk factor	Continuous age at index date.
Gender	Baseline/potential confounder/risk factor	Woman; Male; Unknown.

Variable	Role	Operational definition ^a
Race	Baseline/potential confounder/risk factor	Race recorded.
Hypertension	Baseline/potential confounder	Diagnosis of hypertension within 6 month baseline period.
Hyperlipidemia	Baseline/potential confounder	Diagnosis of hyperlipidemia within 6 month baseline period.
History of coronary artery disease	Baseline/potential confounder	Diagnosis of coronary heart disease within 6 month baseline period.
History of serious infections	Baseline/potential confounder	Hospitalized infections or use of parenteral antibiotics within 6 month baseline period.
History of hospitalization	Baseline/potential confounder	Days hospitalized within 6 month baseline period.
ILD	Comorbidity/Risk factor	Diagnosis of ILD within 6 month baseline period.
Asthma	Comorbidity/Risk factor	Diagnosis or asthma within 6 month baseline period.
VTE	Comorbidity/Risk factor	Diagnosis of PE or DVT within 6 month baseline period.
Cancer	Risk factor	Diagnosis of cancer within 6 month baseline period.
Other immune deficiencies	Risk factor	Diagnosis of immunodeficiency within 6 month baseline period.
HIV/AIDS	Risk factor	Diagnosis of HIV/AIDS within 6 month baseline period.
Diabetes	Risk factor	Diagnosis of diabetes within 6 month baseline period.

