9.7. Data Analysis

After selection of the study population, summary statistics of baseline variables will be determined for the baseline period. The index date for each patient is defined as the first date that the study inclusion criteria are satisfied. Baseline variables will be summarized as

appropriate for categorical and continuous variables with 95% CI provided to show precision of the estimate.

Among patients who are included in the study, outcomes will be included that occur during the risk window from index date until the first of death (based on discharge status), 3 months post-SARS-CoV-2 diagnosis, or end of study period/datacut.

The endpoints of interest within each indication, non-indicated subcohort and indication/treatment combination will be summarized as appropriate for categorical and continuous variables with 95% CI provided to show precision of the estimate.

The handling of missing data will be described in the SAP. No variables will be imputed.

Detailed methodology for summary and statistical analyses of data collected in this study will be documented in a Statistical Analysis Plan (SAP), which will be dated, filed and maintained by the sponsor. The SAP may modify the plans outlined in the protocol; any major modifications of primary endpoint definitions or their analyses would be reflected in a protocol amendment.

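### Two Post-SARS treatment definitions in protocol section 9.3 contradict their sibling rows: the combination row omits tofacitinib and other JAK inhibitors, and the bDMARD row has no time limit

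*Protocol*

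**What the plan says.** A primary objective in section 8 is to "Determine the proportions of patients that continue baseline treatment after SARS-CoV-2 diagnosis within indicated subcohorts". No row in section 9.3 defines continuing. The Post-SARS rows are the only treatment variables measured after index, so the objective presumably rests on them.

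The class rows for csDMARD, TNFi, non-TNFi, tofacitinib and JAK inhibitor all read "Evidence of therapy prescribed within 6 months on or after index date". The bDMARD row reads "Evidence of TNFi or non-TNFi on or after index date". Its baseline counterpart reads "TNFi or non-TNFi prescribed within 6 months prior to index date". The summary row, Post-SARS systemic therapy, reads "Evidence of therapy prescribed within 6 months after index date", which leaves out the index day itself.

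Post-SARS Combination therapy is defined as "Evidence of MTX or other csDMARD concomitant with post-index advanced systemic therapy (ie, bDMARD, tDMARD) and MTX or other csDMARD". Baseline Combination therapy, Post-SARS Monotherapy and the summary row each name tofacitinib and JAK inhibitor.

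The Post-SARS treatment rows carry a baseline or exposure role in the table, although all are measured from the index date onwards.

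**The concern.** This is a safety study of tofacitinib, and the summary row asks for each post-index drug to be classified as monotherapy or combination therapy. If the combination row cannot hold tofacitinib, that classification fails for the study drug while it works for biologics. A before-and-after table would then show patients leaving tofacitinib combination therapy when nothing about their treatment had changed.

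The open bDMARD window acts differently. More follow-up can only add patients to a composite with no end date, whereas the tofacitinib row closes at 6 months. A reader who compares post-index bDMARD use with post-index tofacitinib use would be comparing two lengths of observation as well as two drugs.

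**Working it through.** The protocol states no continuation rate to reproduce. The check sets the rows side by side and then does the calendar arithmetic.

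**Combination status (section 9.3)**

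| Row | Drugs named | Tofacitinib and JAK inhibitor included? |
|---|---|---|
| Baseline Combination | tofacitinib, bDMARD, JAK inhibitor, csDMARD | yes |
| Post-SARS systemic therapy | csDMARD, TNFi, non-TNFi, tofacitinib, JAK inhibitor | yes |
| Post-SARS Monotherapy | TNFi, non-TNFi, tofacitinib, JAK inhibitor | yes |
| Post-SARS Combination | bDMARD, tDMARD | no |

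Take a patient on tofacitinib plus MTX both before and after index.

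1. At baseline the patient is on combination therapy, because tofacitinib is on that list.
2. After index, monotherapy fails because MTX is present.
3. After index, combination fails because tofacitinib is not listed. It cannot enter as a bDMARD, which the table defines as TNFi or non-TNFi, with tofacitinib kept separate. It cannot enter as a tDMARD, which section 2 expands as traditional.

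The list is introduced by ie, not eg, so it reads as complete. Any other JAK inhibitor gives the same result.

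**Time window (section 9.3)**

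| Row | Upper limit |
|---|---|
| Baseline bDMARD | 6 months (before index) |
| Post-SARS TNFi | 6 months |
| Post-SARS non-TNFi | 6 months |
| Post-SARS tofacitinib | 6 months |
| Post-SARS bDMARD | none stated |

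A first post-index TNFi prescription in month 8 makes the patient bDMARD-positive, TNFi-negative and non-TNFi-negative. The composite then exceeds the union of its own parts.

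For a sense of scale only, assume a constant monthly rate r of first post-index prescription. The proportion positive by month t is 1 − exp(−rt).

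| Assumed r per month | By 6 months | By 12 months | Difference (points) |
|---|---|---|---|
| 0.1 | 45.1% | 69.9% | 24.8 |
| 0.2 | 69.9% | 90.9% | 21.0 |
| 0.3 | 83.5% | 97.3% | 13.8 |

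These rates are assumptions, not protocol figures. The direction is certain; the size is not.

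**Who can complete a 6-month window**

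The inputs are a study period of 1 February 2020 to 30 June 2022 and a first cut on 30 April 2020 (section 9.1), and end of data collection on 11 October 2022 (section 6).

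- Study period: 335 days in 2020 + 365 in 2021 + 181 in 2022 = 881 days.
- First cut: at most 89 days after 1 February 2020, so no patient can have 6 months.
- Data to 30 June 2022: index dates after 31 December 2021 fall short, 181/881 = 20.5%.
- Data to 11 October 2022: index dates after 11 April 2022 fall short, 19 + 31 + 30 = 80 days, 80/881 = 9.1%.

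These are shares of calendar days, not of patients.

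**The case against.** The strongest reply is that these are drafting slips with an obvious intended meaning. All five classes in the section 8 treatment objective share one 6-month window. The bDMARD row is only a composite of two capped rows, and the summary row shows that tofacitinib was meant to be classed as monotherapy or combination. Tofacitinib and csDMARD each have their own Post-SARS row, so no prescription is lost. A footnote to section 9.3 sends further definitions to the SAP.

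Much of this stands. It would be wrong to say that windows differ across drugs in general; one composite row differs. It would also be wrong to say that tofacitinib use goes unrecorded. But the footnote defers further detail and does not correct a list and a window already stated. Section 9.8 has analyses programmed to the protocol and, if applicable, the SAP. The title page also names bDMARD as a class in the research question. Counting MTX as its own tDMARD partner does not rescue the combination row, because MTX alone would then qualify as combination therapy.

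A reader might infer three stronger points, which the protocol does not support:

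- **Deaths and short follow-up counted as not continuing.** No text sets the denominator for continuation. The rule that ends at death, "3 months post-SARS-CoV-2 diagnosis, or end of study period/datacut", covers outcomes only, and the SAP may settle the rest.
- **Immortal time bias.** The objectives stratify outcomes by baseline treatment. Nothing plans to stratify 30- or 90-day outcomes by Post-SARS therapy. What remains is a misleading role label.
- **Holding and resuming hidden inside continuing.** Section 7 cites guidance to stop or hold JAK inhibitors on infection, but gives no frequency. Since continuing is undefined, the SAP may still separate the two.

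**Conclusion.** Two rows in section 9.3 are wrong as written. The Post-SARS Combination row leaves every patient on post-index tofacitinib or another JAK inhibitor with a concurrent csDMARD without a category, against three sibling rows. The Post-SARS bDMARD row has no end date, against its two components, its baseline counterpart and the tofacitinib row. A third, lesser fault is the baseline role given to post-index variables.

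The first fault misclassifies the study drug's combination status. The second can only raise the bDMARD proportion relative to a 6-month definition. How many patients either affects cannot be worked out from the protocol. The study is descriptive, so neither type I error nor power is involved; the harm is to the reading of the post-index treatment proportions. The link to the continuation objective is an inference, because these are the only post-index treatment variables. The faults deserve correction but do not undermine the study.

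**What to change.** In section 9.3:

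1. **Post-SARS Combination therapy.** List TNFi, non-TNFi, tofacitinib and JAK inhibitor, as the Post-SARS Monotherapy row does, and delete tDMARD. Baseline Combination carries csDMARD in its own list, so state whether two csDMARDs count as combination therapy and apply the same answer to both rows.
2. **Post-SARS bDMARD.** Add the limit used in the TNFi and tofacitinib rows ("Evidence of therapy prescribed within 6 months on or after index date"), and use the same wording in the Post-SARS systemic therapy row so that the index day is treated alike.
3. **Role column.** Relabel all Post-SARS treatment variables as post-index outcomes.

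When the continuation proportion is reported, show deaths and patients without 6 months of data before the cut as separate lines. This matters most at the early cuts.

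The cost is a few words in the table, two redefined variables and two extra lines in one output. Outputs already produced under the present rows would need those variables rerun. A table based on gaps in supply is not required: it would need an assumed days' supply where only an order is recorded, and it remains a matter of choice.
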